**Table 3. Summary of the Estimand Attributes Corresponding to the Primary Efficacy Objective**

Estimand Label	Attributes of the Estimand				Statistical Summary
	Treatment	Endpoint	Population	Handling of Intercurrent Events	
EASI 90 and WP-NRS 0/1 at Week 16	Upadacitinib vs. dupilumab	Achievement of both EASI 90 and WP-NRS 0/1 at Week 16	Adolescents and adult subjects with moderate to severe AD who have inadequate response to systemic therapy.	Subjects will be considered as non-responders after the initiation of rescue medication (composite variable strategy); and the value for the variable of interest is used regardless of treatment discontinuation (treatment policy strategy).	Difference in the proportion of subjects treated with upadacitinib compared with those treated with dupilumab.

### 9.3.3 Sensitivity and Supplementary Analyses of the Primary Efficacy Endpoint

Sensitivity analysis of the primary efficacy endpoint will be performed by using MI and NRI to handle missing data, respectively.

Supplementary Analysis: supplementary analysis of the primary endpoint will be performed by excluding those subjects whose primary endpoint evaluations were not completed by Blinded Efficacy Assessors or completed by blinded efficacy assessors who

were accidentally unblinded to treatment information. Please refer to Documentation of Key Decision for more details.

## **9.4 Secondary Efficacy Endpoints and Analyses**

### **9.4.1 Key Secondary Efficacy Endpoint(s)**

Ranked Secondary Endpoints are as follows.

1. Achievement of EASI 90 at Week 16.
2. Achievement of WP-NRS 0/1 at Week 16 among subjects with Baseline WP-NRS > 1.
3. Achievement of an improvement (reduction) in WP-NRS  $\geq 4$  at Week 16 among subjects with Baseline WP-NRS  $\geq 4$ .
4. Achievement of WP-NRS 0/1 at Week 4 among subjects with Baseline WP-NRS > 1.
5. Achievement of WP-NRS 0/1 at Week 2 among subjects with Baseline WP-NRS > 1.
6. Achievement of EASI 90 at Week 4.
7. Achievement of EASI 75 at Week 2.
8. Achievement of EASI 100 at Week 16.

### **9.4.2 Main Analyses of Key Secondary Efficacy Endpoint(s)**

In Period 1, the ranked secondary efficacy endpoints will be analyzed by comparing upadacitinib and dupilumab. The categorical endpoints will be analyzed by CMH test on ITT 1 Population, adjusting for vIGA-AD categories (vIGA-AD 3; 4) and age (12 to < 18; 18 to < 40;  $\geq 40$  to < 64 years).

The attributes of the estimands corresponding to the key secondary efficacy objectives are summarized in [Table 4](#).

**Table 4. Summary of the Estimand Attributes Corresponding to the Key Secondary Efficacy Objectives**

Estimand Label	Attributes of the Estimand				
	Treatment	Endpoint	Population	Handling of Intercurrent Events	Statistical Summary
Categorical secondary endpoints	Upadacitinib vs. dupilumab	Achievement of the respective categorical secondary endpoint	Adolescents and adult subjects with moderate to severe AD who have inadequate response to systemic therapy.	Subjects will be considered as non-responders after the initiation of rescue medication (composite variable strategy); and the value for the variable of interest is used regardless of treatment discontinuation (treatment policy strategy).	Difference in the proportion of subjects treated with upadacitinib compared with those treated with dupilumab.

### 9.4.3 Sensitivity and Supplementary Analyses for Key Secondary Efficacy Endpoints

Supplementary Analysis: supplementary analysis of each ranked secondary endpoint will be performed by excluding those subjects whose corresponding ranked secondary endpoint evaluations were not completed by blinded efficacy assessor or were completed by Blinded Efficacy Assessors who were accidentally unblinded to treatment information. Please refer to Documentation of Key Decision for more details.

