Randomization will be stratified by baseline disease severity (moderate validated Investigator Global Assessment for AD [vIGA-AD 3] vs. severe [vIGA-AD 4]) and age categories (12 to < 18; 18 to < 40; \geq 40 to < 64 years).

During Period 1 and Period 2 which are open-label, only the efficacy assessor will be blinded to the subject's treatment assignment. Subjects and other study site personnel will be aware of the subject's treatment assignment.

Further details regarding study procedures are located in the Operations Manual. See Section 5 for information regarding eligibility criteria.

The primary analysis for the study will be performed when all ongoing subjects have completed Week 16 or permanently discontinued Period 1. This analysis is the final and only analysis for the primary and ranked secondary endpoints. Additional analyses may be performed as appropriate.

Figure 1. Study Schematic

BL = Baseline; EOW = every other week; EASI 50/75 = Eczema Area and Severity Index 50/75; QD = once daily; SC= subcutaneous; vIGA-AD = Validated Investigator’s Global Assessment for Atopic Dermatitis

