APPENDIX D. ACTIVITY SCHEDULE

The following table shows the required activities for the study. The individual activities are described in detail in the Operations Manual ([Appendix F](#)).

Study Activities Table

	Screening	Baseline	Week 2	Week 4	Week 8	Week 12	Week 16	Week 20	Week 32	Unscheduled/Premature Discontinuation	12-week follow up Visit/Call (subjects on dupilumab)	30-Day Follow Up Visit/ Call (subjects on upadacitinib)
Activity	Day -35 to Day -1	Day 1	Day 15	Day 29	Day 57	Day 85	Day 113	Day 141	Day 225			
INTERVIEWS & QUESTIONNAIRES												
Visit Window (+/- days)			3				7					
Informed consent/assent	✓											
Eligibility criteria	✓	✓										
Medical/surgical history	✓	✓										
Alcohol, nicotine, drug history	✓	✓										
Prior/concomitant therapy	✓	✓	✓	✓	✓	✓	✓	✓	✓	✓	✓	✓
Latent TB risk assessment questionnaire	✓											
Review and document pregnancy avoidance recommendations (for all subjects of childbearing age)		✓	✓	✓	✓	✓	✓	✓	✓	✓		
Patient Reported outcomes: WP-NRS (assessed daily via a handheld ePRO device)	✓	✓	✓	✓	✓	✓	✓	✓	✓	✓		
For China sites only, dispense subject paper diary cards for adverse event symptoms, concomitant therapy, and investigational product administration		✓	✓	✓	✓	✓	✓	✓	✓	✓		
For China sites only, review adverse event symptoms and concomitant therapy assessment from the subject paper diary cards			✓	✓	✓	✓	✓	✓	✓	✓		

	Screening	Baseline	Week 2	Week 4	Week 8	Week 12	Week 16	Week 20	Week 32	Unscheduled/Premature Discontinuation	12-week follow up Visit/ Call (subjects on dupilumab)	30-Day Follow Up Visit/ Call (subjects on upadacitinib)
Activity	Day -35 to Day -1	Day 1	Day 15	Day 29	Day 57	Day 85	Day 113	Day 141	Day 225			
For China sites only, collect subject paper diary cards for adverse event symptoms, concomitant therapy, and investigational product administration			✓	✓	✓	✓	✓	✓	✓	✓		
EXAMINATIONS												
Body weight	✓	✓	✓	✓	✓	✓	✓	✓	✓	✓		
Height (adult)		✓										
Height (adolescent)	✓	✓			✓		✓		✓	✓		
Tanner staging (adolescent)		✓					✓					
Vital signs	✓	✓	✓	✓	✓	✓	✓	✓	✓	✓		
Physical examination	✓	✓					✓		✓	✓		
Adverse event assessment	✓	✓	✓	✓	✓	✓	✓	✓	✓	✓	✓	✓
12-Lead ECG	✓											
Chest X-ray	✓											
ASSESSOR BLINDED EXAMINATIONS												
EASI	✓	✓	✓	✓	✓	✓	✓	✓	✓	✓		
BSA	✓	✓	✓	✓	✓	✓	✓	✓	✓	✓		

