#### **3.2 Secondary Endpoints**

Ranked Secondary Endpoints are as follows.

1. Achievement of EASI 90 at Week 16.
2. Achievement of WP-NRS 0/1 at Week 16 among subjects with Baseline WP-NRS > 1.
3. Achievement of an improvement (reduction) in WP-NRS  $\geq 4$  at Week 16 among subjects with Baseline WP-NRS  $\geq 4$ .
4. Achievement of WP-NRS 0/1 at Week 4 among subjects with Baseline WP-NRS > 1.
5. Achievement of WP-NRS 0/1 at Week 2 among subjects with Baseline WP-NRS > 1.
6. Achievement of EASI 90 at Week 4.
7. Achievement of EASI 75 at Week 2.
8. Achievement of EASI 100 at Week 16.

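### The blinded-assessor exclusion in SAP 9.3.3 and 9.4.3 has no carve-out for self-reported itch, and for EASI it drops randomized subjects when only the rating is compromised

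*SAP*

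**What the plan says.** SAP 9.4.3 states: "supplementary analysis of each ranked secondary endpoint will be performed by excluding those subjects whose corresponding ranked secondary endpoint evaluations were not completed by" a blinded efficacy assessor, or were completed by one who was accidentally unblinded. The operative condition is that the subject's "endpoint evaluations were not completed by blinded efficacy assessor". SAP 9.3.3 uses the same rule for the primary endpoint, "excluding those subjects whose primary endpoint evaluations were not completed by Blinded Efficacy Assessors". Neither section makes an exception for any endpoint. Both end by deferring to another document: "Please refer to Documentation of Key Decision for more details". That document is not part of the protocol or the SAP.

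Four of the eight ranked endpoints in SAP 3.2 are itch endpoints. Rank 2 is "Achievement of WP-NRS 0/1 at Week 16 among subjects with Baseline WP-NRS > 1". Rank 3 begins "Achievement of an improvement (reduction) in WP-NRS" and requires at least 4 points at Week 16. Ranks 4 and 5 are WP-NRS 0/1 at Weeks 4 and 2. The primary endpoint combines EASI 90 with WP-NRS 0/1.

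Protocol Appendix D lists itch among the patient-reported outcomes: "WP-NRS (assessed daily via a handheld ePRO device". The same table puts only EASI, BSA and vIGA-AD under assessor-blinded examinations. Protocol 4.1 adds that "only the efficacy assessor will be blinded to the subject's treatment assignment"; subjects know what they receive.

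SAP 4.0 assigns all efficacy analyses to the ITT populations. The SAP version history shows that these supplementary analyses were added in version 4.0 of the SAP.

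**The concern.** There are two separate problems.

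The first is scope. The rule asks whether a blinded assessor completed the evaluation. For WP-NRS the answer is no for every subject at every visit, because the subject completes it. The rule therefore cannot be run as written on the itch endpoints or on the composite.

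The second is method. Who rated a subject, and whether that rater had been unblinded, is known only after randomization. Removing the subject, and not just the doubtful rating, means the arms compared are no longer the arms randomized. The wording also leaves open what happens to a subject with no EASI at the visit. No blinded assessor completed an evaluation for that subject either, so the subject could be dropped here or kept as a non-responder under SAP 9.2.

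This matters because the other planned checks on the primary endpoint (NRI and MI, SAP 9.3.3) address missing data. This is the only listed check on compromised blinding in a trial whose efficacy claim rests partly on a blinded assessor, so it should be runnable and interpretable from the SAP alone.

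**Working it through.** **Step 1. Apply the rule to each endpoint.** Endpoints are from SAP 3.1 and 3.2; the rater is from Protocol Appendix D.

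| Endpoint | Measure | Completed by | Left under the literal rule |
|---|---|---|---|
| Primary | EASI 90 and WP-NRS 0/1, Week 16 | assessor and subject | none, if both halves must qualify |
| Rank 1 | EASI 90, Week 16 | assessor | subjects with a blinded rating |
| Rank 2 | WP-NRS 0/1, Week 16 | subject | 0 of about 880 |
| Rank 3 | WP-NRS reduction of at least 4, Week 16 | subject | 0 of about 880 |
| Rank 4 | WP-NRS 0/1, Week 4 | subject | 0 of about 880 |
| Rank 5 | WP-NRS 0/1, Week 2 | subject | 0 of about 880 |
| Rank 6 | EASI 90, Week 4 | assessor | subjects with a blinded rating |
| Rank 7 | EASI 75, Week 2 | assessor | subjects with a blinded rating |
| Rank 8 | EASI 100, Week 16 | assessor | subjects with a blinded rating |

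So 4 of 8 ranked analyses, and the composite, have no analysable subject on a literal reading.

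**Step 2. Is power the issue?** SAP 2.4 gives 440 per arm, 12% against 12% + 17% = 29%, two-sided 0.05, and more than 90% power. With pooled variance under the null:

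- null SE = √(2 × 0.205 × 0.795 / 440) = 0.0272
- alternative SE = √((0.12 × 0.88 + 0.29 × 0.71) / 440) = 0.0266
- (0.17 − 1.96 × 0.0272) / 0.0266 ≈ 4.38, so power is 0.99999

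The plan's figure is reproduced. Excluding 10% of each arm (396 left) gives 0.99997, and excluding 20% (352 left) gives 0.9999. Loss of power is not the concern.

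**Step 3. How large could selection bias be for EASI?** The documents give no exclusion rate, so everything here is assumed. Let the true response be p = 20.5% in both arms (the midpoint of 12% and 29%), with a fraction f excluded from each arm. Let excluded upadacitinib subjects respond at p − δ and excluded dupilumab subjects at p + δ. The retained rates are (p − f(p − δ))/(1 − f) and (p − f(p + δ))/(1 − f), so

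spurious difference = 2fδ/(1 − f).

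At f = 10% and δ = 10 points this is 2 × 0.10 × 0.10 / 0.90 = 2.2 points. The rejection rate is the chance that a normal variable centred at difference/SE falls outside ±1.96, with 440(1 − f) per arm.

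| f | Difference, δ = 5 | Rejection | Difference, δ = 10 | Rejection |
|---|---|---|---|---|
| 2% | 0.2 points | 5.1% | 0.4 points | 5.3% |
| 5% | 0.5 points | 5.4% | 1.1 points | 6.6% |
| 10% | 1.1 points | 6.7% | 2.2 points | 12.1% |
| 20% | 2.5 points | 13.0% | 5.0 points | 37.7% |

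If exclusion is unrelated to arm and outcome (δ = 0), the bias is zero.

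**Step 4. Would NRI be a safe replacement?** Keep 20.5% in both arms, and let 5% of upadacitinib and 10% of dupilumab ratings be compromised, unrelated to outcome (also assumed). Counting these as non-response gives 20.5 × 0.95 = 19.5% against 20.5 × 0.90 = 18.5%. That is a spurious difference of about 1.0 point in favour of upadacitinib, where exclusion would give none. NRI favours whichever arm has fewer compromised ratings.

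**The case against.** The strongest reply is that nobody would apply the rule to itch. Appendix D separates assessor-rated from patient-reported measures, and both SAP sections send the reader to a key-decision document where the affected evaluations would be expected. A programmer would meet an ambiguity and ask; four empty tables would not be delivered. This stands as a prediction. It does not repair the SAP text, which names every ranked endpoint and leaves the limit to a document outside it.

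A reader might go further and infer that the rule breaks randomization or abandons ITT for the trial. The documents do not support that. The primary and ranked tests stay on ITT 1 (SAP 9.1, 9.3.2, 9.4.2), the hierarchical testing in SAP 13.0 is unchanged, and the SAP labels the analysis supplementary. Nor do they say why an assessor might be unblinded, other than by accident, or that it happens more in one arm. The figures in step 3 need excluded subjects to deviate in opposite directions by arm.

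A reader might also suppose that an itch endpoint listed under this rule has a blinded version. The protocol rules that out, since subjects know their treatment and report itch themselves.

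Finally, it can be said that imputing is only a preference over excluding, and that MI assumes missing at random (SAP Appendix H, 2.2), which may fail if compromised ratings relate to outcome. The second half is right and should be stated. But MI keeps all randomized subjects and uses their other EASI visits, which exclusion discards.

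**Conclusion.** The point holds as a defect of specification with a better method at hand. On the SAP text alone, the supplementary analyses of ranks 2 to 5 and of the primary composite cannot be carried out. That the sponsor intends EASI only is likely but unstated. For the EASI endpoints the planned subset is not protected by randomization. Any bias is possible, not shown, and of unknown size; it depends on how many ratings are compromised and on how that relates to arm and outcome. At small exclusion rates it would be modest even under adverse assumptions. No confirmatory result, sample size or error rate changes, so the priority is low.

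**What to change.** Amend SAP 9.3.3 and 9.4.3 as follows.

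- Limit the rule to assessor-rated EASI: ranks 1, 6, 7 and 8, and the EASI component of the primary. State that the WP-NRS endpoints have no blinded-assessor version.
- Keep all ITT 1 subjects. Set only the compromised EASI ratings to missing and impute them with the MI model already in SAP 9.2 and Appendix H. For the composite, a subject with an observed WP-NRS above 1, or with rescue, remains a known non-responder whatever the EASI.
- Say that a subject with no EASI rating at all is handled as in the main analysis.
- Report the number of compromised ratings by arm and visit.
- State that MI rests on missing at random. If NRI is also shown, do not call it conservative, for the reason in step 4.
- Correct the responder line in the Appendix H sample code before reuse. `WK16<=0.9*BASE` flags a 10% reduction: at a baseline EASI of 16, the minimum for entry, it counts 14.4 or less as response, whereas EASI 90 needs 1.6 or less.

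The cost is a short SAP amendment, slightly more analysis work, and reliance on the missing-at-random assumption for the affected ratings.

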### 9.5 Additional Efficacy Endpoints and Analyses

CMH test will be used to analyze categorical variables stratified by vIGA-AD categories (vIGA-AD 3; 4) and age (12 to < 18; 18 to < 40;  $\geq$  40 to < 64 years). NRI-MI will be used for handling missing data. All variables in [Section 3.1](#), [Section 3.2](#), and [Section 3.3](#) will

also be summarized descriptively in Period 2 using the OC approach. Models of categorical variables in Period 1 and Period 2 are summarized in [Table 2](#).

## 9.6 Efficacy Subgroup Analyses

To evaluate the consistency of efficacy over demographic and other Baseline characteristics, the primary efficacy endpoint will be analyzed in the following subgroups.

- Baseline vIGA-AD (3;4),
- Baseline EASI score ( $< 21$ ;  $\geq 21$ ),
- Baseline EASI score ( $< \text{median}$ ;  $\geq \text{median}$ ), and
- Age (12 to  $< 18$ ; 18 to  $< 40$ ;  $\geq 40$  to  $< 64$  years).

Of note, any subgroups with fewer than 10% subjects may be combined with other for analyses, and the 10% cutoff may be updated after running the baseline characteristics. For any subgroup, if there are zero subjects within a stratum in any treatment group, the CMH model will not be adjusted for the stratification factors. For each type of subgroup, Breslow-Day test will be performed to test the homogeneity across subgroups.

## 9.7 Analysis of Daily Efficacy Measurement for Worst Pruritus NRS

For daily efficacy assessments of the Worst Pruritus NRS, a rolling weekly average is calculated by using handheld device only to represent the corresponding endpoints by week in Period 1 and 2.

The weekly average of the daily values from a maximum of seven days immediately prior to the first dose date will be used as the Baseline value. The rolling weekly average score is calculated for each Day  $m$ , starting from Day 8 through the Week 16 visit as follows. Let  $P_{m-6}, P_{m-5}, \dots, P_{m-1}, P_m$  be the daily score from Day  $m-6$  to Day  $m$ , and  $N_m$  be the number of days with non-missing scores from Day  $m-6$  to Day  $m$ , then the rolling weekly average for Day  $m$  is:

$$\frac{\sum_{i=m-6}^m P_i}{N_m}$$

If the values from four or more days of the seven-day period are missing, then the rolling weekly average of Day  $m$  will be set to missing. If more than one assessment is included on the same day, the assessment associated with the worst condition on that day will be chosen as the daily score. Analysis value for a given visit will be selected from rolling averages based on analysis window conventions.

For the visits where the questionnaire is completed at the site, scores from single clinic visits will be used as the analysis value. However, these analysis values will not be included in rolling weekly average calculations.

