## **2.4 Sample Size Determination**

Approximately 880 subjects will be randomized to upadacitinib or dupilumab in a 1:1 ratio. Assuming a response rate of 12% in achieving both EASI 90 and WP-NRS 0/1 at Week 16 in the dupilumab arm, this sample size will provide more than 90% power to detect the treatment difference of 17% (upadacitinib versus dupilumab), using a two-sided significant level of 0.05. Sample size calculations were performed using nQuery Version 9.1.1.0.

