## **9.2 Handling of Missing Data**

In Period 1, missing values and visits after the rescue will be handled by non-responder imputation (NRI) except for missing values due to COVID-19 or any other missing data that can be reasonably assumed to be Missing at Random, which will be handled by multiple imputation (NRI-MI).

- The NRI-MI will categorize any subject who does not have an evaluation during a pre-specified visit window (either due to missing assessment or due to early withdrawal from the study) as a non-responder for the visit. The only exceptions are: 1) when the subject is a responder both before and after the visit window, the subject will be categorized as a responder for the visit. 2) missing data due to COVID-19 infection or logistical restriction or any other missing data that can be reasonably assumed to be Missing at Random, will be handled by Multiple Imputation. In addition, all assessments after the start of rescue medications will not be included in the analyses; as a result, subjects will be counted as non-responders thereafter and will not be imputed by MI. Random seeds are provided in [Appendix D](#). NRI-MI is the primary approach to handle missing data for categorical endpoints in Period 1.
- Non-responder Imputation (NRI): NRI will be performed in the same way as NRI-MI without the exception #2 above. That is, missing due to COVID-19 infection or logistical restriction or any other missing data that can be reasonably assumed to be Missing at Random, will also be counted as non-responders. The NRI is a missing data handling method in a sensitivity analysis for the primary endpoint.

Subjects whose change/percent change from Baseline cannot be calculated because of a missing Baseline will be considered as a non-responder at all post-baseline visits in both NRI-MI and NRI approaches.

Multiple Imputation (MI): another missing data handling method performed in a sensitivity analysis for the primary endpoint. Markov Chain Monte Carlo (MCMC) will be first applied to augment data into monotonic missing pattern and PROC MI will be used to generate 30 datasets using the regression method.

- The imputation is done in two steps for the primary endpoint.
- Step 1: The EASI 90 and WP-NRS 0/1 (based on weekly average) are imputed separately.

For example, for EASI 90, the variables to be included in the imputation model are treatment group, major stratum (vIGA-AD categories and age),

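### SAP 9.7 lets a single site-completed itch score stand as a visit's WP-NRS value without limiting it to non-confirmatory visits, against the weekly-average definition used elsewhere

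*SAP*

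**What the plan says.** SAP 9.7 sets the measure for daily itch: "a rolling weekly average is calculated by using handheld device only", and gives both study periods as its scope. Baseline is the average of up to seven days before first dose. The formula runs from Day 8 through the Week 16 visit, an average with four or more of its seven days missing is set to missing, and visit values are picked from the rolling averages.

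The section then ends with a different rule: "For the visits where the questionnaire is completed at the site, scores from single clinic visits will be used as the analysis value". The sentence after it keeps such scores out of the rolling average.

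Elsewhere the weekly average is the only definition. SAP 9.2, on imputing the primary endpoint, says "The EASI 90 and WP-NRS 0/1 (based on weekly average) are imputed separately". The Protocol's Study Activities Table (Appendix D) lists "WP-NRS (assessed daily via a handheld ePRO device") at every visit from screening through Week 32 and at unscheduled or discontinuation visits. It names no on-site mode.

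**The concern.** WP-NRS is one half of the primary endpoint and the whole of ranked secondaries 2 to 5. The on-site sentence is a positive instruction and is not confined to Period 2 or to descriptive summaries. If it were triggered at Week 2, 4 or 16, three things would follow.

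- **Two definitions of response.** A score of 0 or 1 on one day is a different, and usually easier, target than a 7-day mean of at most 1.
- **Mismatched change scores.** For ranked secondary 3, a one-day score would be compared with a 7-day baseline.
- **A way round the missing-data rule.** A subject with too few handheld scores has a missing average and is a non-responder under NRI-MI unless one of its two exceptions applies. One clinic score could make that subject an itch responder.

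The planned checks would not expose this. The NRI and MI sensitivity analyses (SAP 9.3.3) change only how missing values are treated, so they would carry the same clinic scores. The supplementary analysis concerns the blinded efficacy assessor, not the way the subject's own itch score is collected.

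**Working it through.** **Inputs from the documents (SAP 2.4).** "Approximately 880 subjects will be randomized to upadacitinib or dupilumab in a 1:1 ratio", so 440 per arm. "Assuming a response rate of 12% in achieving both EASI 90 and WP-NRS 0/1 at Week 16 in the dupilumab arm". The plan is to "detect the treatment difference of 17% (upadacitinib versus dupilumab), using a two-sided significant level of 0.05", so 12% v 29%. Stated power: "this sample size will provide more than 90% power".

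**Assumed inputs.** The documents give no spread for WP-NRS and no on-site frequency. Assumed: between-subject SD 2 to 2.5, day-to-day SD 0.5 to 1.5, independent days, integer scores 0–10. The 12% and 29% are composite rates, borrowed here for itch alone.

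**Step 1: reproduce the plan's figure.** SE = √(0.12×0.88/440 + 0.29×0.71/440) = 0.0266. Power = Φ(0.17/0.0266 − 1.96) = Φ(4.43) > 0.9999. With pooled variance it is also 0.99999. The stated power is correct and conservative: 117 per arm would give 90%.

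**Step 2: compare the two measures.** 400,000 subjects were simulated per setting, with the mean set so that P(7-day mean ≤ 1) was 12% or 29%. The last day alone was then scored as ≤ 1.

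| Between / daily SD | Single score, 12% arm | Single score, 29% arm | Difference |
|---|---|---|---|
| 2 / 0.5 | 17.4% | 36.9% | 19.4 |
| 2 / 1.0 | 19.7% | 38.8% | 19.1 |
| 2 / 1.5 | 23.8% | 42.2% | 18.4 |
| 2.5 / 0.5 | 16.1% | 35.2% | 19.1 |
| 2.5 / 1.0 | 17.7% | 36.7% | 19.0 |
| 2.5 / 1.5 | 20.9% | 39.6% | 18.7 |

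(Differences are from unrounded rates.) Between 5% and 15% of subjects change status in the lower-rate arm, and 7% to 20% in the other. If days are strongly correlated (assumed 0.8, day-to-day SD 0.7 to 1.5), a single score adds about 4 to 8 points, so the direction holds and the gap narrows.

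**Step 3: equal on-site use.** With share f in both arms, difference = (1−f)×17.0 + f×(single-score difference). At f = 0.10: 0.9×17.0 + 0.1×18.4 = 17.1, up to 0.9×17.0 + 0.1×19.4 = 17.2. Power stays above 0.9999. Under the null, both arms shift equally and rejection stays at 5.0%.

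**Step 4: on-site use that differs by arm, no true effect.** Bias = (f_upa − f_dup) × (p_single − p_average), with the average-based rate 12% in both arms and between-subject SD 2.2.

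| Daily SD | p_single | Bias, 0% v 20% | Rejection | Rejection, 5% v 15% |
|---|---|---|---|---|
| 0.5 | 16.9% | 0.20×4.9 = 1.0 | 7.3% | 5.6% |
| 1.0 | 18.8% | 0.20×6.8 = 1.4 | 9.3% | 6.1% |
| 1.5 | 22.3% | 0.20×10.3 = 2.1 | 14.9% | 7.4% |

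Rejection = 1 − Φ(1.96 − bias/SE) + Φ(−1.96 − bias/SE). In the last row, SE = 0.0227 for the 0% v 20% split, so bias/SE is about 0.91.

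**Step 5: a higher itch rate.** Itch alone cannot have a lower response rate than the composite. With a 20% average-based rate in both arms, the 0% v 20% split gives bias 1.2 to 2.4 points and rejection 7.4% to 14.0%, much as before.

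**The case against.** The strongest case against is that the documents, read together, already specify the weekly average for every confirmatory WP-NRS endpoint. The Protocol names daily handheld collection only. SAP 9.7 runs the rolling average through the Week 16 visit. SAP 9.2 describes the Week 16 component as weekly-average based. SAP Appendix D lists random seeds for WP-NRS at weeks with no clinic visit, which presupposes daily data. Because the formula stops at Week 16, the on-site sentence may serve only Weeks 20 and 32, where results are descriptive.

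Most of this stands, and it rules out several stronger inferences.

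- A reader might infer that the primary endpoint does mix two measures. Nothing shows that any Week 2, 4 or 16 score is completed on site. The Operations Manual, to which the Protocol refers for detail, is not among the documents.
- A reader might infer that the clinic score overrides an existing weekly average. The SAP is silent on priority; this is one reading of that silence.
- A reader might infer that clinic scores are worse because the subject knows the treatment. Handheld scores come from the same unblinded subject. The open-label design means only that on-site use differing by arm cannot be excluded.

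What does not stand is the step from likely intent to adequate text. The Period 2 reading is nowhere stated. It sits badly with the section's own scope of both periods and with handheld collection scheduled at Weeks 20 and 32.

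**Conclusion.** SAP 9.7 contains an unrestricted rule that conflicts with the weekly-average definition in the same section, in SAP 9.2 and at baseline. It should be corrected, but the consequence is conditional on on-site completion at a confirmatory visit, which the documents do not show.

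If such completion happens equally in both arms, the harm is negligible: 0.1 to 0.2 points on the difference at 10% use, no inflation of type I error, and power unaffected. Harm to the comparison requires on-site use that differs by arm. At an assumed 0% v 20%, bias is about 1 to 2 points and null rejection about 7% to 15%; at 5% v 15%, rejection is about 6% to 7%. These figures are for itch alone. Requiring EASI 90 as well would be expected to reduce them for the composite, by an amount not calculated here. All sizes rest on the assumed SDs and on-site shares. The direction, with the single score giving the higher rate, held in every setting tested.

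**What to change.** In SAP 9.7, state that the primary endpoint and ranked secondaries 2 to 5 use only the handheld rolling weekly average, with at least 4 of 7 daily scores. Where that average is unavailable, treat WP-NRS as missing and apply NRI-MI as in SAP 9.2. Show any clinic scores at those visits only in a listing or a sensitivity analysis.

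Deleting the on-site sentence outright would go too far, since it may be the only rule giving a value at Weeks 20 and 32. If it is kept, limit it to named non-confirmatory visits (for example Period 2), and extend the rolling-average formula beyond the Week 16 visit so that it matches the section's stated scope of both periods.

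The cost is a few lines of SAP text. The 4-of-7 threshold and NRI-MI are already in the plan, and no sample-size figure changes. The downside is possibly a few more missing WP-NRS values; the number cannot be estimated from the documents.
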